## **1.2 Secondary and Other Objectives**

There are no secondary or other objectives for this study.

## **2 Analysis Populations and Data Conventions**

### **2.1 Analysis Populations**

Two populations will be used in the statistical analysis: safety population and modified intent-to-treat (mITT) population. If any patient is mis-stratified by the site at randomization on day 1, this patient's data will be included in the stratum to which the patient should have been stratified instead of the interactive voice response system (IVRS) stratum for analysis.

The safety population will include all treated patients based on the treatment received. All safety analyses will be based on the actual treatment received by each patient in this population.

The mITT population will include all randomized patients with a valid MAS-B baseline ankle score with knee extended and at least one post-baseline measurement at weeks 2, 4, or 6 for the MAS-B ankle score with knee extended and the Clinical Global Impression of Overall Change (CGI) by Physician. Here weeks 2, 4, and 6 refer to the analysis visits defined in Section 2.2. The mITT population will be analyzed according to randomization assignment, regardless of treatment actually received. Efficacy data, demographics, and background information will be analyzed on the basis of the mITT population.

### **2.2 Treatment Visits**

All days are referenced to day 1. Day 1 is the randomization/treatment day. In the cases where randomization and treatment happened on different days, the day of treatment will be used as day 1. Visits according to the windows below will be determined for each variable analyzed unless noted otherwise in the following sections. If there are values from multiple visits in a given window, the value collected from the visit closest to the target day will be used to represent the window. If 2 visits with values fall within the same window and are equidistant from the target day, the value from the first of the 2 visits chronologically will be used to represent the window. For clinical laboratory variables, the last non-missing observation for that visit window will be used. This rule will be applied separately for each variable for non-missing data only.

(The exception is because re-runs of laboratory variables may only involve one or a few variables and would thus include missing data for many variables).

Visit	Target Day of the Visit	Visit Window (Day*)
Screening	-28	$\leq$ Day -1
Day 1 (Randomization/Treatment)	1	Day 1
Week 2	15	Day 2 to Day 22
Week 4	29	Day 23 to Day 36
Week 6	43	Day 37 to Day 50
Week 8	57	Day 51 to Day 71
Week 12	85	$\geq$ Day 72

\* All days are referenced to day 1. For post-treatment visits, study day = visit date - day 1 date+1 while for pre-treatment visits, study day = visit date - day 1 date.

The visit windows will be used for by-visit analyses in both modified intent-to-treat (mITT) and safety population analyses.

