12.1.4 Hematology and Serum Chemistry

During screening, patients will need to have a blood sample for laboratory evaluations collected after informed consent is signed. Another blood sample will be collected at the study exit visit. Blood specimens will be collected using standard laboratory instructions and procedures provided by the central laboratory. Fasting blood samples should be collected

BOTOX® (Botulinum Toxin Type A) Purified Neurotoxin Complex

unless the patient is not able to fast for approximately 8 hours. Patients who are willing to fast and did not come to the screening visit in a fasting state may return prior to the day 1 visit for blood sample collection as long as the laboratory results can be received and reviewed at or before the day 1 visit. The blood specimens will be analyzed for the following:

Hematology	hemoglobin	hematocrit	red blood cells
	white blood cells	neutrophils	bands
	lymphocytes	monocytes	basophils
	eosinophils	platelets	
Electrolytes	sodium	potassium	bicarbonate
	chloride	phosphorus	calcium
Chemistry	glucose	creatinine	urea nitrogen
	total bilirubin	alkaline phosphatase (total plus bone and liver fractions)	aspartate aminotransferase (serum glutamic oxaloacetic transaminase)
	alanine aminotransferase (serum glutamic pyruvic transaminase)	albumin	
Other	HbA1c	25 hydroxyl vitamin D	Parathyroid hormone if alkaline phosphatase bone fraction is abnormal

Reference ranges for alkaline phosphatase and glucose are shown in Table 5.

Table 5 Reference Ranges for Alkaline Phosphatase and Glucose

Parameter	Age (Years)	Range
Alkaline phosphatase		
Female	1 to 3	125 to 320 U/L
	4 to 6	150 to 370 U/L
	7 to 9	150 to 440 U/L
	10 to 11	150 to 530 U/L
	12 to 13	110 to 525 U/L
	14 to 15	55 to 305 U/L
	16 to 19	40 to 120 U/L
Male	1 to 3	125 to 320 U/L
	4 to 6	150 to 370 U/L
	7 to 9	150 to 440 U/L
	10 to 11	150 to 470 U/L
	12 to 13	160 to 500 U/L
	14 to 15	130 to 530 U/L
	16 to 19	60 to 270 U/L
Bone-specific alkaline phosphatase (ostase)		
Female	1 to 6	0 to 189 U/L
	7 to 9	0 to 246 U/L
	10 to 13	0 to 340 U/L
	14 to 15	0 to 91 U/L
	≥ 16	0 to 55 U/L
Male	1 to 6	0 to 208 U/L
	7 to 9	0 to 264 U/L
	10 to 15	0 to 340 U/L
	16 to 19	0 to 165 U/L
Glucose	All ages	70 to 100 mg/dL, 3.9 to 5.6 mmol/L

Note: Reference ranges were received from Covance Laboratory as of 16 January 2012.

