- Data from unscheduled visits or re-test visits will be treated the same way as scheduled visits, ie, the dates of such visits will be used in the categorization of visit window. The algorithm handling multiple visits within a visit window will also be applied to unscheduled visits and re-test visits.
- For the primary and secondary efficacy analyses where study center is a factor in the analysis model, centers that recruited only a few patients will be pooled together. The following algorithm for pooling study centers will be used:
  - A. Pooling of study centers will by country.
  - B. Within each country, the following will be conducted:

1. Study centers will be ranked in descending order of the total number of patients enrolled.
2. Any center with at least 12 patients will stand on its own.
3. The first center with fewer than 12 patients will be combined with the next center until the total number in the pooled center reaches or exceeds 12 patients.
4. The algorithm of combining centers will continue down the list as described above.
5. If the last pooled center still has less than 12 patients, the last pooled center will be combined with the previous pooled center.

C. If there are less than 12 subjects enrolled in a country, the country will be pooled to the smallest center in the same region (alphabetical order if there is a tie). The regions include Asia-Pacific, Europe, and North America. For example, if Canada enrolled less than 12 patients, Canada will be pooled with a smallest center in the United States.

- The mean change from baseline for a given treatment group will be calculated by taking the sum of all individual changes from baseline divided by the number of patients with observations in that treatment group. As a consequence, patients without the particular follow-up data will not be taken into account, except if there is a missing value replacement method used.

|

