## 6.4 Clinical Laboratory Evaluations

Hematology and non-fasting clinical chemistry assays will be obtained at screening and exit as specified below.

Hematology	hemoglobin	hematocrit	red blood cells
	white blood cells	neutrophils	bands
	lymphocytes	monocytes	basophils
	eosinophils	platelets	
Electrolytes	sodium	potassium	bicarbonate
	chloride	phosphorus	calcium
Chemistry	glucose	creatinine	urea nitrogen
	total bilirubin	alkaline phosphatase (total plus bone and liver fractions)	aspartate aminotransferase (serum glutamic oxalacetic transaminase)
	alanine aminotransferase (serum glutamic pyruvic transaminase)	albumin	
Other	hemoglobin A1c	25 hydroxyl vitamin D	Parathyroid hormone if alkaline phosphatase bone fraction is abnormal

These values at each visit and the change from baseline will be summarized by the treatment group by visits using descriptive statistics. All laboratory values will be listed. Laboratory values at each visit will also be categorized as low, normal, and high according to the respective reference normal ranges.

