## **6.6                    Columbia-Suicide Severity Rating Scale**

Suicidality for age over 6 years will be assessed using the Columbia-Suicide Severity Rating Scale (C-SSRS), conducted at every assessment visit. Suicide-related events corresponding to the C-SSRS questions will be classified into the following 11 categories:

- Self-injurious behavior, no suicidal intent
- Suicidal ideation
  1. Wish to be dead
  2. Active: Nonspecific (no method, intent, or plan)
  3. Active: Method, but no intent or plan
  4. Active: Method and intent but no plan
  5. Active: Method, intent and plan
- Suicidal behavior
  1. Preparatory acts or behaviors
  2. Aborted attempt
  3. Interrupted attempt
  4. Suicide attempt
  5. Completed suicide

The number and percentage of patients with the above suicide-related events during treatment will be presented by treatment group. If a patient has more than one suicide-related event during an interval, the most severe event in increasing order listed above will be used.

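### SAP 2.2 keeps the last laboratory value in a window, so a normal re-test can remove an abnormal exit value from the low/normal/high table; add an any-low/any-high table

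*SAP*

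**What the plan says.** Most variables follow one rule in SAP 2.2 when several visits fall in a window: "the value collected from the visit closest to the target day will be used to represent the window". Laboratory data are an exception: "For clinical laboratory variables, the last non-missing observation for that visit window will be used". The reason given is that "re-runs of laboratory variables may only involve one or a few variables". The Week 12 window starts at Day 72 and has no end.

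SAP 2.3 then adds: "The algorithm handling multiple visits within a visit window will also be applied to unscheduled visits and re-test visits".

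The Protocol schedules blood at screening and, in section 12.1.4, "Another blood sample will be collected at the study exit visit". Each patient therefore has one planned post-injection laboratory sample.

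On reporting, SAP 6.4 says "All laboratory values will be listed" and "Laboratory values at each visit will also be categorized as low, normal, and high according to the respective reference normal ranges". It plans no table of the worst value or of any abnormality. Protocol 7.3.4 also plans a shift table of out-of-range values against baseline, and optional reporting of potentially clinically significant values. SAP 6.4 mentions neither, although SAP 12 declares no deviations from the protocol.

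**The concern.** A valid laboratory result is usually repeated because it was abnormal; a normal exit result gives little reason for another draw. A rule that keeps the later value therefore tends to replace abnormal with normal when it acts on exit re-tests. The stated reason does not require this. That re-runs cover only some analytes justifies choosing the value separately for each variable, which SAP 2.2 already does on non-missing data. It does not justify setting aside an earlier valid result.

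At stake is the count of patients per arm with an out-of-range laboratory value after injection, in a paediatric trial whose stated objective includes safety. A transient abnormality that has resolved by the re-test would not appear in the SAP 6.4 categories for that arm.

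**Working it through.** The documents give no abnormality, re-test or normalisation rate, so there is no planned figure to reproduce. The check applies the SAP 2.2 windows to example pairs and then derives the size of the loss.

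**Step 1: apply the rule.** The relevant windows are Week 4 (Days 23 to 36), Week 6 (Days 37 to 50) and Week 12 (Day 72 onward, target Day 85).

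| Exit value | Re-test | Last value (SAP rule) | Closest to target day | Any abnormal value |
|---|---|---|---|---|
| Day 85 high | Day 95 normal | normal | high | high |
| Day 78 high | Day 88 normal | normal | normal | high |
| Day 30 high (early exit) | Day 34 normal | normal | high | high |
| Day 34 high (early exit) | Day 44 normal | high in Week 4, normal in Week 6 | same | high |

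The abnormal value is lost in the first three rows. In the fourth the two samples fall in different windows and both are tabulated. Row two shows that switching to the closest-to-target rule would not reliably solve the problem: Day 88 is 3 days from target and Day 78 is 7.

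**Step 2: size.** Let p be the share of patients abnormal at exit, r the share of those re-tested in the same window, and q the share of those re-tests that are normal.

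- Tabulated share = p × (1 − r × q)
- Share of abnormal patients lost = r × q

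All three are assumptions. With p = 10% and, for scale only, the 117 completers per arm in Protocol 7.5, 11.7 patients per arm are truly abnormal:

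| r | q | Lost (r × q) | Tabulated, of 11.7 |
|---|---|---|---|
| 0 | any | 0% | 11.7 |
| 0.10 | 0.25 | 2.5% | 11.4 |
| 0.50 | 0.50 | 25% | 8.8 |
| 0.90 | 0.75 | 67.5% | 3.8 |

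**Step 3: effect on the comparison.** Take assumed true rates of 6% and 2%, with r × q = 0.35 in both arms. The tabulated rates are 6% × 0.65 = 3.9% and 2% × 0.65 = 1.3%. The difference falls from 4.0 to 2.6 percentage points. The ratio stays at 3 (6/2 = 3.9/1.3).

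**The case against.** The strongest reply is that the triggering event is not shown to be common. No post-exit laboratory repeat is scheduled. Protocol 8.7 treats the last visit as the exit visit, and patients who continue go straight to day 1 of the extension study (Protocol 8.3.5), so a later draw may belong to that study. Unscheduled samples before Day 72 sit in their own windows and are not overwritten by a Week 12 exit value. This stands as a limit on size. It does not remove the mechanism: Protocol 8.5 allows unscheduled visits for safety concerns and requires a case report form for each, and SAP 2.2 and 2.3 expressly provide for re-runs and re-test visits.

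A reader might infer several stronger things that the documents do not support:

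- **That low/normal/high is the only categorical laboratory summary planned.** It is the only one in SAP 6.4, but Protocol 7.3.4 also plans a shift table. That table would have the same gap if built on windowed values.
- **That a resolved abnormality survives only in listings.** Under Protocol 9.1.1 an abnormal laboratory finding can be an adverse event, and SAP 6.2 tabulates treatment-emergent events. That route depends on the investigator's judgement.
- **That the rule always works one way.** Baseline is also the last value before treatment (SAP 2.3). A normal screening repeat makes baseline normal and can increase apparent shifts to abnormal, so the net effect on a shift table can go either way. The direction is clear only for post-injection counts after an exit re-test.
- **That the SAP contradicts itself** because SAP 6.6 says "the most severe event in increasing order listed above will be used" and SAP 6.2 takes the worst severity. Those are summaries of events. SAP 6.4 summarises a measurement by visit, where one value per window has to be chosen. The last value is a defensible convention for that purpose, and the natural choice when a faulty sample is re-run.

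**Conclusion.** The point holds as a gap in safety reporting, of minor priority. As written, an abnormal exit value followed by a normal re-test in the same window is counted as normal in the SAP 6.4 categories.

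The loss is r × q of abnormal patients. Nothing in the documents fixes r or q, so no particular percentage can be claimed: it is zero without recorded re-tests and 2.5% to 67.5% across the assumed grid. Nor can a distorted ratio between arms be claimed: with blinded arms re-tested alike the ratio is preserved, and only counts and absolute differences shrink. The efficacy analyses are unaffected.

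**What to change.** Keep the last-value rule in SAP 2.2 for by-visit means, change from baseline and by-visit categories. Add to SAP 6.4 a table by treatment group, for each laboratory variable, of patients with any low and any high post-injection value. Use all reported scheduled, unscheduled and re-test results, and show the baseline category. Reporting low and high separately avoids having to define a most abnormal value.

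The cost is a sentence in the SAP, derived flags and one extra table, from data already collected. Reported abnormality counts will be somewhat higher: relative to the exit-re-test loss above, by a factor of 1/(1 − r × q), for example from 8.8 back to 11.7 patients when r × q = 0.25. Patients sampled more often have more chances to be counted, which a footnote should state.

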7.5 Sample Size Calculation

Approximately 412 patients will be enrolled to ensure that at least 351 patients (117 per treatment group) will complete the study.

Using a 2-sample t-test, a significance level of 0.05, and the assumptions in Table 4, the power for MAS-B change from baseline is 94% (PASS, Hintze, 2008). The calculation is based on assumptions for 8 U/kg group and placebo group. Since there are 2 co-primary endpoints for the US FDA analysis, for 8 U/kg group the power for CGI by Physician is calculated to be 97%, and the overall power for the US FDA co-primary endpoints will be at least 91%. The assumptions for MAS-B were based on results of completed Studies BTX108509 and BTX108512; the estimates for CGI were based on results of completed Study 191622-021.

Table 4 **Sample Size Assumptions and Power Calculations**

Endpoint	Average of Week 4 and 6 for 8 U/kg group	Average of Week 4 and 6 for Placebo group	Standard Deviation	Power
MAS-B Change from Baseline	-0.8	-0.45	0.75	94%
CGI by Physician (Co-primary for US FDA Analysis)	1.2	0.6	1.2	97%
Overall Endpoints				91%

CGI = Clinical Global Impression of Overall Change; MAS-B = Modified Ashworth Scale – Bohannon; US FDA = United States Food and Drug Administration

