8.7 Early Discontinuation of Patients

Patients may voluntarily withdraw from the study at any time or may be withdrawn at the discretion of the investigator and Allergan due to clinically significant findings including, but not limited to, adverse events and clinical laboratory abnormalities. Allergan will be notified of early patient discontinuation from the study and the reason for discontinuation will be clearly documented on the appropriate eCRF.

The last visit for the patient will be considered the study exit visit. Procedures for week 12 will be performed if the study exit visit occurs earlier than week 12.

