## **6.7                   Immunogenicity Testing**

Blood samples (approximately 7 mL per visit) will be collected for immunogenicity testing at the screening visit and study exit from patients who weigh at least 15 kg at the screening visit. A 2-stage assay approach will be used for the detection of binding antibodies against BoNT-A and neutralizing antibodies against BOTOX in patients' serum. In stage 1, serum samples will be screened for reactivity using a validated enzyme-linked immunosorbent assay (ELISA). The reactive serum samples will be subsequently titered to assess the extent of antibodies present and immunodepleted to confirm that the reactivities are specific to BoNT-A. In stage 2, only samples that are confirmed positive in the ELISA will be tested for neutralizing antibodies to BOTOX using a validated assay.

Immunogenicity results of binding antibodies (BABs) against BoNT-A will be reported as positive or negative. Immunogenicity results of neutralizing antibodies (NABs) against BOTOX will be reported as positive, negative, or inconclusive. For NABs, the total negatives including patients with negative neutralizing antibody results as well as with negative binding antibody results will be reported.

Immunogenicity findings will be tabulated with the number and percent of patients at each visit separately for each treatment group. Percentages will be based on the number of treated patients with interpretable antibody assays in each treatment group at the specified visit. Antibody titers will be summarized by median, minimum, and maximum.

Depending on the timing and availability of data, immunogenicity data may be locked separately, at a different time point following the database lock for the main clinical data.

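### The SAP visit windows have no exit row, so laboratory samples from early-termination visits before day 72 fall into Week 2 to 8 rows and the Week 12 laboratory row covers only patients seen from day 72 on

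*SAP*

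**What the plan says.** **Visit labelling.** SAP 2.2 gives the default rule: "Visits according to the windows below will be determined for each variable analyzed unless noted otherwise in the following sections". On scope it adds: "The visit windows will be used for by-visit analyses in both modified intent-to-treat (mITT) and safety population analyses". The rows are Screening, Day 1, Week 2 (days 2 to 22), Week 4 (days 23 to 36), Week 6 (days 37 to 50), Week 8 (days 51 to 71) and Week 12 (day 72 or later). There is no exit or early-termination row. The section names clinical laboratory variables and takes their latest available value in a window. SAP 2.3 places unscheduled and re-test visits by date as well.

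**Early exit.** Protocol 8.7 says: "Procedures for week 12 will be performed if the study exit visit occurs earlier than week 12". Under Protocol 8.3.5 those procedures include blood for hematology, chemistry and HbA1c. Patients who weighed at least 15 kg at screening also give blood for immunogenicity.

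**Summaries.**
- Laboratory (SAP 6.4): assays at screening and exit. "These values at each visit and the change from baseline will be summarized by the treatment group by visits using descriptive statistics". Low, normal and high categories are also given per visit.
- Antibodies (SAP 6.7): samples at screening and study exit. "Immunogenicity findings will be tabulated with the number and percent of patients at each visit separately for each treatment group". Percentages are based on treated patients with an interpretable assay at the visit in question.
- Vital signs and weight (SAP 6.5): taken at screening, day 1 and exit, with the change from baseline to the exit visit named as a summary.

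**The concern.** Each patient has one scheduled post-treatment laboratory sample, at exit. If the date decides the row, that sample is filed by when the patient left. Most patients go to Week 12, and those who left earlier are spread over four rows that the schedule does not intend for laboratory data.

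The only well-filled post-treatment laboratory row is then restricted to patients who stayed until day 72. Protocol 8.7 names adverse events and laboratory abnormalities among the reasons for withdrawal, so early leavers may differ from stayers in the very values being summarised. Nothing later in the plan brings them back: SAP 2.3 does not impute missing laboratory values, and it computes mean change only from patients with the follow-up value. At stake is whether the end-of-study laboratory comparison between arms, and possibly the antibody comparison, includes everyone who gave an exit sample.

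**Working it through.** **1. The plan's own figures.** Protocol 7.5 states: "Approximately 412 patients will be enrolled to ensure that at least 351 patients (117 per treatment group) will complete the study".
- With 117 per group, a two-sided 0.05 two-sample t-test and Table 4 (difference 0.35, SD 0.75 for MAS-B; difference 0.6, SD 1.2 for CGI), the noncentral t distribution gives 94.5% and 96.8%. The plan states 94% and 97%.
- The product is 0.945 × 0.968 = 91.4%; the plan states 91%.
- An allowance of 15% gives 351 / 0.85 = 412.9, in line with about 412.

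The plan's figures reproduce. They matter here only as the source of the counts below.

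**2. Where an exit sample goes.** Study day = visit date − day 1 date + 1 (SAP 2.2).

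| Exit on study day | Row under SAP 2.2 | Laboratory draw scheduled then? |
|---|---|---|
| 2 to 22 | Week 2 | no |
| 23 to 36 | Week 4 | no |
| 37 to 50 | Week 6 | no |
| 51 to 71 | Week 8 | no |
| 72 or later | Week 12 | yes |

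A patient who leaves 39 days after injection is on day 40, so the exit sample becomes a Week 6 value.

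**3. Is an exception noted?**
- SAP 6.4: no. Exit is the sampling time, but the summary is by visit and no exit row is named.
- SAP 6.7: unclear. Only screening and study exit are named before the tabulation is described, so the visits meant could be those two or the window rows.
- SAP 6.5: yes, for change from baseline. However, SAP 2.2 defines no exit analysis visit for it to use.

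**4. How many patients.** Assume that all 412 are treated and that completers are sampled on day 72 or later.
- Planned non-completers: 412 − 351 = 61; 61 / 412 = 14.8%; 61 / 3 = 20.3 per arm.
- If all of them leave before day 72 and give a sample, spread evenly: 20.3 / 4 = about 5 per arm per row.
- An exit row would raise the end-of-study laboratory count from 351 (117 per arm) to at most 412 (about 137 per arm).

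The documents do not give the number of early-exit samples or their days, so the range at the planned loss is 0 to 61. Antibody numbers are lower because of the 15 kg limit.

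**5. What it could do to a rate (assumed rates, illustration only).** Let 5% of stayers have an abnormal exit value and a share r of leavers. The Week 12 row shows 5.0% whatever r is. An exit row shows (351 × 0.05 + 61 × r) / 412:
- r = 5%: (17.55 + 3.05) / 412 = 5.0%
- r = 10%: (17.55 + 6.10) / 412 = 5.7%
- r = 20%: (17.55 + 12.20) / 412 = 7.2%

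If leavers and stayers have the same rate, the difference is zero.

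**The case against.** The windows apply only where later sections do not say otherwise, and those sections are written around exit. Laboratory tests, vital signs and antibodies are all scheduled at it, Protocol 8.7 treats a patient's last visit as the exit visit, and Protocol 8.3.5 covers week 12 and early termination together. An analyst could take this as the exception. For antibodies that reading is at least as natural as the other, so the point is only a possibility there. For laboratory tests it is weaker: SAP 2.2 names laboratory variables as subject to windows, and naming a sampling time in 6.4 does not redefine the analysis visit. SAP 6.5 shows that an exit summary was written out where one was intended.

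A reader might infer that the whole end-of-study safety summary leaves out early leavers, or that their results disappear. The documents do not support either. Adverse event and serious adverse event tables cover all treated patients without visit windows. Vital signs and weight have a named change to exit. C-SSRS events are counted over the treatment period. All laboratory values are listed, early-exit values still appear in their own rows, and Protocol 7.3.4 evaluates out-of-range values per patient in shift tables. An abnormal laboratory finding can also be recorded as an adverse event.

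It is also fair to say that labelling by actual day is legitimate after a single injection, that these tables are descriptive, and that 61 is a planning allowance. These objections limit the size of the point. They do not supply the missing exit row.

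**Conclusion.** The point holds for laboratory tests. By the stated default rule, early-termination samples before day 72 go to Week 2 to 8 rows with no scheduled draw, and the Week 12 row represents only patients seen from day 72. For antibodies the SAP does not settle the question.

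At the planned loss the effect is at most 61 of 412 patients (14.8%, about 20 per arm), provided that every non-completer leaves before day 72 and gives a sample. It is smaller if some do not, and would be larger only if attrition exceeded the plan. Any shift in an abnormality rate depends on how leavers differ from stayers. The documents do not say, so the 5.0% to 7.2% range is not a forecast. The point does not reach the primary endpoint, power, adverse event tables or the vital signs and weight change to exit. This is a cheap improvement, not a threat to the trial's conclusions.

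**What to change.** - **SAP 2.2:** add an Exit analysis visit, defined as the value from the week 12 or early-termination visit, ie the last post-treatment value.
- **SAP 6.4 and 6.7:** state that laboratory and antibody summaries, change from baseline and the low, normal and high categories are reported at Exit, and that this overrides the date windows.
- **SAP 6.5:** refer to the same definition for the change in vital signs and weight to exit.
- **Efficacy scales:** leave the date windows as they are.

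The cost is one table row, a sentence in each of three sections and a small programming change, with no new data collection. The downside is that an Exit row pools samples taken at different times since injection. Keep the windowed Week 12 row beside it, so that readers can see both the complete set and the set at a comparable time.
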